SBRT is planned for the tumor location as a dose of 5 fractions of 10-12 Gy or 3 fractions of 18-20 Gy (Phase 2 only). SBRT fractions will be given sequentially, and within 180 minutes from the end of the GC4711 or placebo infusion. Between fractions, a minimum of 18 hours and a maximum of 96 hours are permitted. All fractions should be given within 10 calendar days (+3 days in the case of a holiday or technical issue).

Phase 1: In the Phase 1 portion, 5 subjects will each receive 100 mg of GC4711 by 15-minute IV infusion, before each SBRT fraction, beginning the day of the first fraction and ending the last day of SBRT (5 doses in total). SBRT is administered within 180 minutes (3 hours) of the end of the GC4711 infusion.

All 5 subjects will be monitored for dose limiting toxicity (DLT) occurring during treatment with SBRT and GC4711 or within 30 days post-therapy. DLT is defined (using the National

Cancer Institute–Common Terminology Criteria for Adverse Events (NCI-CTCAE) grading scale) as Grade 3-5 AEs occurring from Day 1 to 30 days post SBRT completion, and *excluding* the following:

- AEs clearly related to disease progression or intercurrent illness
- Grade 3 fatigue for 7 days or less,
- Grade 3 nausea/vomiting or diarrhea for less than 72 hours with adequate antiemetic and other supportive care
- Grade 3 or higher amylase or lipase that is not associated with symptoms or clinical manifestations of pancreatitis
- Hematological grade 3-4 toxicities except for the following:
 - Grade 4 neutropenia lasting >7 days.
 - Grade 3 thrombocytopenia with clinically significant bleeding.
 - Grade 4 anemia and grade 4 thrombocytopenia

Safety will be judged unacceptable if 2 or more (i.e., no more than one) of the 5 subjects develop a DLT. Safety will be reviewed by a Safety Review Committee (SRC) consisting of the Medical Monitor, the Principal Investigator from each Phase 1 site, and additional designees by the Sponsor or the site Principal Investigators.

Phase 2: After the SRC has confirmed acceptable safety for Phase 1, a Phase 2, randomized, placebo-controlled study will be initiated, wherein approximately 66 subjects referred for SBRT with early stage large and/or central localized NSCLC will be randomized in a 1:1 ratio to receive either GC4711 100 mg or placebo given intravenously (IV) over 15 minutes before each fraction of SBRT, beginning the day of the first fraction of SBRT and ending the last day of SBRT.

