4. Prior intra-thoracic radiotherapy or surgery with substantial overlap to **planned** radiation fields as determined by the treating radiation oncologist.
5. Subjects not recovered/controlled from prior treatment-related (chemotherapy or targeted therapy) toxicities judged by treating physician.
6. Uncontrolled malignancy other than lung cancer that requires active treatment or is deemed by the treating physicians to be likely to affect the subject's survival duration.
7. History of allergic reactions attributed to compounds of similar chemical or biologic composition to GC4711.
8. Uncontrolled intercurrent illness including, but not limited to, active infection, symptomatic congestive heart failure, unstable angina pectoris, cardiac arrhythmia, or psychiatric illness/social situations that, in the opinion of the investigator, would limit compliance with study requirements.
9. Participation in other clinical trials actively testing new anti-cancer treatments, unless previously written approval is provided by the Sponsor.

10. Requirement for concurrent treatment with nitrates or other drugs that may, in the judgment of the treating investigator, create a risk for a precipitous decrease in blood pressure.
11. Female subjects who are pregnant or breastfeeding.
12. Any other conditions that, in the Investigator's opinion, might indicate the subject to be unsuitable for the study.

Duration of Treatment:

Phase 1: SBRT is administered in 5 sequential fractions of 10-12 Gy with each fraction preceded by once daily (QD) doses of GC4711 (5 doses) from the start to the last fraction

Phase 2: SBRT is administered in 5 sequential fractions of 10-12 Gy or 3 sequential fractions of 18-20 Gy with each fraction preceded by once daily (QD) doses of GC4711/placebo (3 or 5 doses) from the start to the last fraction

Reference Therapy, Dosage and Mode of Administration:

Phase 1 will use open-label GC4711 to be given as a 15-minute, 100 mL IV infusion. GC4711 100 mg QD should be completed within 180 minutes prior to SBRT (5 doses).

Phase 2 will include two treatment arms:

- **Arm A:** GC4711 100 mg (15 min, 100 mL IV infusion to complete within 180 minutes prior to SBRT) administered before each SBRT, from the first dose of SBRT to the last fraction of SBRT.
- **Arm B:** Placebo (15 min, 100 mL normal saline IV infusion) given in combination with SBRT as described for Arm A. Normal saline should be provided by the site's unblinded pharmacists.

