Hydrogen peroxide is more toxic to tumor cells than to normal cells. This cancer cell sensitivity may reflect lower expression levels of catalase, glutathione peroxidase and other enzymes that degrade hydrogen peroxide in the cancer cell (Oberley 1997), a translocation of catalase (Bohm 2015), or susceptibility of cancer metabolism. In irradiated tissue, radiation directly and indirectly generates additional superoxide which is then converted by SOD enzyme or dismutase mimetic to additional hydrogen peroxide. The amount of superoxide generated is related to RT fraction dose size, and thus the amount of hydrogen peroxide produced by the dismutase mimetic is also proportional to fraction dose size. As hydrogen peroxide increases with fraction dose size, it can reach levels that have significant anti-tumor effects (Greenberger 2007, Sishc 2018, Sishc 2019). For example, the overexpression of manganese SOD (MnSOD, or SOD2) by plasmid liposomes in multiple mouse organs was shown to protect normal cells from radiation damage while increasing the radio-sensitivity of tumor cells, indicating that normal cells were protected from superoxide damage while tumor cells were susceptible to hydrogen peroxide (Greenberger 2007).

[figure not shown]

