6.2 Stereotactic Body Radiation Therapy (SBRT)

SBRT Dosage, Administration, and Schedule

Patients will be evaluated by the treating radiation oncologist at the local site. Based on location and size of the tumor, dose planning will be determined by clinical appropriateness that balances ablation of the lesion(s) while respecting normal tissue constraints including for ultra-central lesions the volume criterium of the contoured proximal bronchial tree less than 0.03cc =<52.5Gy (Bejzak 2019).

Table 2 Organ Constraints for a 3-Fraction SBRT Regimen

Serial Tissue	Volume (cc)	Volume Max (Gy)	Max Point Dose (Gy) ²	Endpoint (\geq Grade 3)
Esophagus ¹	<5	27.9	32.4	Esophagitis
Brachial Plexus	<3	22	26	Neuropathy
Heart/Pericardium	<15	24	30	Pericarditis
Great vessels	<10	39	45	Aneurysm
Trachea and Large Bronchus ¹	<5	39	43	Impairment of pulmonary toilet
Bronchus smaller airways	<0.5	25.8	30	Stenosis with atelectasis
Rib	<5	40	50	Pain or fracture
Lung (Right & Left)	1500 for males; 950 for females ³	10.8		Basic Lung Function
Lung (Right & Left)			V-11.4Gy<37%	Pneumonitis
Spinal cord	<0.35	15.9	22.5	Myelitis

Abbreviations:

1. Avoid circumferential irradiation

2. “point” defined as 0.035cc or less

3. or one-third of the “native” total organ volume (prior to any resection or volume reducing disease), whichever is greater:

- Exceeding these dose tolerances by more than 2.5% constitutes a minor protocol violation.

- Exceeding these dose tolerances by more than 5% constitutes a major protocol violation.

Table 3 Organ Constraints for a 5-Fraction SBRT Regimen

Serial Tissue	Volume (cc)	Volume Max (Gy)	Max Point Dose (Gy) ²	Endpoint (\geq Grade 3)
Esophagus ¹	<5	32.5	38	Esophagitis
Brachial Plexus	<3	27	32.5	Neuropathy
Heart/Pericardium	<15	32	38	Pericarditis
Great vessels	<10	47	53	Aneurysm
Trachea and Large Bronchus ¹	<5	45	50	Impairment of pulmonary toilet
Bronchus smaller airways	<0.5	32	40	Stenosis with atelectasis
Rib	<5	45	57	Pain or fracture
Lung (Right & Left)	1500 for males; 950 for females ³	12.5		Basic Lung Function
Lung (Right & Left)			V-13.5Gy<37%	Pneumonitis
Spinal cord	<0.35	22	28	Myelitis

Abbreviations:

1. Avoid circumferential irradiation
2. “point” defined as 0.035cc or less
3. or one-third of the “native” total organ volume (prior to any resection or volume reducing disease), whichever is greater:
 - Exceeding these dose tolerances by more than 2.5% constitutes a minor protocol violation.

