8.2 Randomization/Blinding

Phase 1:

The Phase 1 part of the study will be conducted as an open-label investigation.

Phase 2:

In the Phase 2 of the study, all subjects, investigators, clinical study site personnel and the blinded study monitor will be blinded to patient treatment assignment.

The dispensing Site Pharmacists are unblinded. An unblinded Study Monitor will be assigned to the study for confirming drug accountability and monitoring at the site's pharmacy. The Unblinded Pharmacist should take every precaution to prepare the study treatment in a blinded fashion and out of site from the Blinded site clinical staff. The Blinded Clinical Staff should be mindful of the steps in place to maintain the blind.

Treatment assignment for Phase 2 subjects should remain blinded to subjects, investigators, and clinical site staff until analyses of the primary and secondary safety and efficacy results of the study have been performed on the final, locked data through the end of post-SBRT follow-up for all subjects.

Only in the case of an emergency, when knowledge of the investigational product is essential for the clinical management or welfare of the subject, may the Investigator unblind an individual subject's treatment assignment prior to the completion of the primary and secondary safety and efficacy analyses. The Investigator will, whenever possible, discuss options with the Medical Monitor or appropriate Sponsor/CRO study personnel before unblinding. If the blind is broken for any reason and the Investigator is unable to contact the Sponsor prior to unblinding, the Investigator must notify the Sponsor/CRO as soon as possible following the unblinding incident without revealing the subject's study treatment assignment, unless the information is important to the safety of subjects remaining in the study.

Randomization codes are generated and assigned using a Randomization and Trial Supply Management (RTSM) system. Electronic access to the randomization codes will be granted for unblinded pharmacy team members and unblinded CRAs.

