8.5 Statistical Analyses

The statistical analysis plan will be finalized prior to database lock and will include a more detailed description of the statistical analyses described in this section. Should the statistical analysis plan and the protocol differ with respect to analytic conventions, the statistical analysis plan supersedes the protocol. Given the study has not been powered for formal hypotheses testing, all P-values should be considered descriptive in nature. As such no alpha adjustment for multiple testing is planned.

All time to event endpoints will be measured from date registration (Phase 1) or randomization (Phase 2).

Primary Endpoints:

Phase 1: DLT defined in Section 7.5.

Phase 2: The difference in in-field tumor response between GC4711 and placebo through Month 6 following SBRT will be estimated, and a two-sided 90% confidence interval constructed around the difference using the large sample confidence interval with limits $\pm Z.05 \sqrt{[(p1*(1-p1)/n + p2*(1-p2)/m)]}$ of the point estimate where p1 and p2 are the response rates and n and m the corresponding number of patients in each arm. In addition, a Fisher's Exact test will be performed but should be considered descriptive in nature. Phase 2: Percent reduction of in-field tumor response at Month 6 compared to baseline.

Secondary Efficacy Endpoints:

Phase 1: All Phase 1 efficacy endpoints will be summarized descriptively.

Phase 2: Response rate (PR+CR at any time during the study) per RECIST 1.1 will be compared using the same methodology as the primary endpoint.

In-field tumor response at Months 6, 12, 18 and 24 will be compared for the two treatment arms using a t-test at each timepoint and corresponding two-sided 90% confidence intervals constructed about the difference. The maximum reduction for each patient observed at any time will be analyzed similarly.

Progression-free survival (PFS) will be compared using a hazard ratio along with the associated 2-sided 90% confidence interval, using an un-stratified Cox's proportional hazard model and further characterized by Kaplan-Meier curves as well as the median and survival probability at

representative times (e.g. at 2, 4, 6, 4 etc. months). A log-rank test comparing treatment arms based on the score statistic from the Cox regression will also be provided. Patients who have not progressed or died will be censored at their last evaluable response assessment.

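### Radiation regimen (3 or 5 fractions) is not used in the Phase 2 randomisation or response analysis, which gives up some protection against chance imbalance and leaves unclear which regimen the estimate describes

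*Combined protocol and SAP*

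**What the plan says.** - **Allocation.** The Synopsis says that Phase 2 patients "will be randomized in a 1:1 ratio to receive either GC4711 100 mg or placebo given intravenously (IV) over 15 minutes before each fraction". Section 4.1 repeats the 1:1 ratio. Section 8.2 adds only this on method: "Randomization codes are generated and assigned using a Randomization and Trial Supply Management (RTSM) system". None of these places names a stratification factor.
- **Two regimens.** The Synopsis (Duration of Treatment) allows five fractions of 10-12 Gy or three of 18-20 Gy in Phase 2. Study drug precedes every fraction, so the regimen fixes the number of infusions: "GC4711/placebo (3 or 5 doses) from the start to the last fraction".
- **Who chooses.** Section 6.2 (SBRT) gives the planning to the local radiation oncologist, on tumour location and size: "dose planning will be determined by clinical appropriateness". Section 2.1 links three fractions to larger peripheral lesions and says that practice is moving to five for central ones.
- **Rationale.** Section 2.2 says that "the amount of hydrogen peroxide produced by the dismutase mimetic is also proportional to fraction dose size".
- **Analysis.** In Section 8.5 the primary analysis is an unadjusted difference in proportions with a 90% large-sample interval and a descriptive Fisher test. PFS is compared "using an un-stratified Cox" model, and OS and local and regional control follow the same approach. No response analysis by regimen is described. In Section 3, dosimetry enters only the exploratory lung-injury risk analysis.

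**The concern.** The regimens differ in dose per fraction, number of fractions and number of infusions, and the choice depends on tumour features. Regimen is therefore a plausible prognostic factor. If the drug's action rises with fraction size, as Section 2.2 argues, it is also a plausible effect modifier.

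With about 33 patients per arm, simple allocation can leave the arms with noticeably different regimen mixes, and the planned analyses make no allowance for that. Section 8.1 also says that the trial should supply efficacy data for planning later studies. A single pooled difference over an unplanned mix does not tell a planner which regimen it describes. The same applies to safety, since the Phase 1 treatment schedule uses five fractions only.

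**Working it through.** **1. The plan's own figure.** Section 8.1 gives a maximum 90% half-width of 21.2% with 30 per arm. At p1 = p2 = 0.5: 1.645 × √(0.25/30 + 0.25/30) = 21.2 points. It reproduces.

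**2. Inputs not in the documents.** Neither the share on three fractions (s) nor response by regimen is given. I assume s = 20-50%, a response gap between regimens (g) of 10, 20 or 30 points, and, for step 5, 40% response on five fractions.

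**3. Chance imbalance at 33 per arm.** The 3-fraction counts in the two arms are taken as independent binomials. The SD of the between-arm difference in share is √(2s(1−s)/33). A gap of 15 points means 5 or more patients (5/33 = 15.2%).

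| s | SD (points) | P(gap ≥ 15 points) |
|---|---|---|
| 20% | 9.8 | 16% |
| 30% | 11.3 | 23% |
| 40% | 12.1 | 26% |
| 50% | 12.3 | 27% |

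Fixing the total number of 3-fraction patients instead (hypergeometric) gives 18-33%, which leads to the same reading.

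**4. Effect on the primary difference.** Shift = imbalance × g. For a 15-point imbalance: 0.15 × 10 = 1.5, 0.15 × 20 = 3.0 and 0.15 × 30 = 4.5 points. These are 7%, 14% and 21% of 21.2.

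**5. Precision.** With 30 per arm, the same response in both arms and balanced strata, write p5 = 0.40, p3 = 0.40 + g and pm = s·p3 + (1−s)·p5.
- Crude half-width: 1.645 × √(2·pm(1−pm)/30).
- Stratified half-width: 1.645 × √(2·[s·p3(1−p3) + (1−s)·p5(1−p5)]/30).

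| g | Crude, s = 20-50% | Stratified | Gain |
|---|---|---|---|
| 10 points | 21.0-21.1 | 20.9-21.0 | about 0.1 |
| 20 points | 21.1-21.2 | 20.8 | 0.3-0.4 |
| 30 points | 21.1-21.2 | 20.1-20.5 | 0.6-1.0 |

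If the regimens respond equally, the gain is zero.

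**6. Interim look.** Section 8.7 plans an unblinded efficacy look at 20 patients. With 10 per arm assumed, a gap of 20 points or more (2 or more patients) has probability 39% at s = 20%, rising to 50% at s = 50%. A 20-point gap shifts the difference by 2, 4 or 6 points for g = 10, 20 or 30. The largest half-width at that look is 1.645 × √(0.5/10) = 36.8 points.

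**The case against.** The strongest reply is that nothing here invalidates the comparison, and that is correct. Four stronger readings are tempting, and the documents support none of them.

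- **That the crude difference is biased or its interval wrong.** Allocation is random, so imbalance averages to zero, and the crude interval already carries the variance from regimen mix. What remains is efficiency and protection in this one sample.
- **That unequal drug exposure confounds the arms.** Placebo patients receive no GC4711. The mix of three and five infusions (300 or 500 mg in total) changes which average effect is estimated. It is not a confounder between arms.
- **That the protocol expects response to differ by regimen.** Section 2.2 supports possible modification of the drug effect. It says nothing about response to SBRT alone by regimen, so any gap is an assumption, and a small one leaves little to correct.
- **That regimen cannot be used as a baseline factor afterwards.** No passage requires it to be recorded before assignment. But Table 1 (footnote e) places randomisation after screening and within 7 days of first SBRT, Sections 6 and 8.2 keep the treating staff blinded, and the choice rests on baseline tumour features. A plan documented before the first infusion has little route to depend on arm.

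It is also fair to say that the trial is not powered for testing and its P-values are descriptive, so a shift of a few points would not change its reading. Regimen partly stands in for tumour location and size. Section 8.5 also defers detail to a later analysis plan that supersedes the protocol. That plan could add adjustment and reporting by regimen, but it could not restore stratified allocation.

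**Conclusion.** The point holds as a modest design weakness. Two physician-planned regimens are pooled, and regimen appears in neither the randomisation nor the response and time-to-event analyses, although the protocol gives reasons to think it may matter.

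Under the assumed 20-50% share, a regimen gap of 15 points or more between arms is not rare (16-27%), and a 15-point gap moves the primary difference by 1.5-4.5 points for response gaps of 10-30 points. The precision gain from stratified analysis runs from about 0.1 to 1.0 point on a half-width of about 21. Imbalance is more likely at the 20-patient look, where the interval is also much wider. All of these sizes depend on the assumed share and response gap. What does not depend on them is the loss of clarity: as planned, the results would not show how response or safety looked under each regimen.

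**What to change.** 1. **Section 8.2:** enter the planned regimen (3 or 5 fractions) in the RTSM before the assignment is released, and stratify the 1:1 randomisation on it.
2. **Section 8.5:** estimate the primary difference as a Mantel-Haenszel risk difference with a 90% interval, stratified by planned regimen, and stratify the log-rank and Cox analyses in the same way.
3. **Reporting:** show response and safety by regimen, descriptively.

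If randomisation has begun, items 2 and 3 can still be done, using the regimen documented before the first infusion rather than the one delivered.

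The cost is one RTSM field and some analysis-plan wording, with no added patients or procedures. The regimen must be declared before assignment, and the 3-fraction stratum may be small, so its separate results will be imprecise.

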2 INTRODUCTION

2.1 Radiotherapy for Non-Small Cell Lung Cancer

Lung cancer is the leading cause of death in the United States, with approximately 135,000 deaths predicted in 2020 ([Ettinger 2020](#)). As recently as 2015, the 5-year survival rate for non-small cell lung cancer (NSCLC) was 25% ([Ettinger 2020](#)). While surgery for early-stage disease remains the preferred treatment, advances in noninvasive treatment modalities, such as targeted therapy, immunotherapy, and modified forms of radiotherapy (RT), have contributed to improved outcomes ([Ettinger 2020](#)). Stereotactic body radiotherapy (SBRT; also known as stereotactic ablative radiotherapy, or SABR) is an RT regimen that targets tumors with image-guided, short dose-intensive ablative courses of radiation, in contrast to conventionally fractionated RT ([Timmerman 2010](#)). SBRT is a current accepted alternative for surgery of peripheral lung lesions ([Stephans 2018, Timmerman 2010, Prezzano 2019](#)) and can be an alternative for larger or central tumors in a 5-fraction regimen in more fragile patients for whom chemo-radiation or surgery presents too great a risk of complications ([Peterson 2016, Bezjak 2019, Ettinger 2020](#)).

Modern RT techniques have enabled more precise delivery of high ablative doses with improved sparing of surrounding normal tissue. For early stage NSCLC, SBRT has become increasingly used as standard of care ([Timmerman 2018](#)). After initial demonstration of safety with SBRT for small peripheral NSCLC lesions, SBRT has been delivered to larger and more central lesions ([Bezjak 2019](#)), which identified SBRT dosing of 11.5 or 12 Gy x 5 fractions as associated with acceptable toxicity and with approximate 2-year rates for local control, overall survival, and progression-free survival of approximately 90%, 70%, and 55%, respectively. Use of SBRT for larger or centrally located NSCLC is reported to increase the risk of toxicity with a larger volume of normal tissue exposure ([Fakiris 2009, Woody 2015, Peterson 2016, Bezjak 2019](#)). SBRT can induce serious inflammatory reactions depending on dose and volume given to the lung and generate fibrosis and lung functional restrictions ([Lu 2018](#)). SBRT delivering a Biological Equivalent Dose of over 100 Gy to the lung is associated with grade 2 or worse pneumonitis in approximately 15% of patients ([Lu 2018](#)).

Individual risk of radiation-induced pneumonitis depends on the volume of lung treated and the radiation dose administered, as well as patient characteristics and other treatment modalities used (immunotherapy itself has around 10% pneumonitis risk on its own ([Mohamad 2018](#))). The risk of clinical pneumonitis requiring medical intervention has been reported to be 9% to 28% after lung SBRT ([Kang 2015, Palma 2013, Yamashita 2014, Timmerman 2018](#)). Many more patients show radiological changes, which can often disturb response evaluation, as well as show milder changes which itself can limit retreatments for metastatic disease in the same lung ([Larici 2011, Kang 2015](#)). Significant (\geq grade 3) rates of pneumonitis have been reported varying from >10% to 21% ([Timmerman 2006, Baumann 2009, Stephans 2018](#)). Chemotherapy or/and immunotherapy carry their own pneumonitis risk and cumulative pneumonitis risk together with SBRT is observed and feared ([Zhao 2016, Mohamad 2018, Palma 2013](#)).

With improved systemic treatment, lung cancer patients are also living long enough to manifest late pulmonary toxicity after RT ([Larici 2011](#)). Moreover, in patients with recurrent disease, re-challenging RT also becomes technically possible. Based on nonclinical data, fibrosis obtained following the first SBRT treatment can significantly limit future treatment options. Due to their close relation to major airways, esophagus and major vessels, central tumors have a higher complication risk from radiotherapy, and are in general treated with 5 or more fractions of SBRT ([Lo 2009](#)) allowing normal tissue in the field more time to repair ([Timmerman 2006](#)).

In this trial, we target larger and/or central tumors associated with a higher pneumonitis and local failure risk, as well as a more fragile patient population. A sequential SBRT regimen of 5 fractions or 3 fractions for larger peripheral lesions delivering dose up till biologically equivalent (total) dose (BED) of 100Gy aligns with the standard dose for larger and/or central lesions ([Bejzak 2015](#), [Timmerman JAMA 2010](#)). The practice is shifting toward 5 fractions specifically for central localizations; however, for larger peripheral lesions, a 3-fraction regimen is still accepted.

The RTOG 0813 trial identified SBRT dosing of 11.5 or 12 Gy x 5 fractions as associated with acceptable toxicity and with approximate 2-year rates for local control, overall survival, and progression-free survival of approximately 90%, 70%, and 55%, respectively ([Bezjak 2019](#)). Other studies ([Stone 2015](#), [Mohamad 2018](#)) reported control rates around 70% and PFS 50-60% at 2 years.

Radiation-induced lung injury is a slowly developing process, mostly manifesting as radiological changes only and transient symptoms around 4-6 months (mean 135 days) after treatment ([Jain 2018](#), [Ferrero 2015](#)). Clinically scored and symptomatic pneumonitis is seen in approximately 10% of patients 6 months after SBRT ([Kang 2015](#), [Yamashita 2014](#), [Mohamad 2018](#)). [Stone et al \(2015\)](#) referred to DLCO decline as the most objective measure of lung toxicity, referring to an observed decline (grade 1 or more) in 20-30% of patients. While a small decline is not seen as clinically significant, it is predictive for more severe accumulative toxicity risk in cases of pre-existing lung disease or in those with subsequent need for re-treatment in the thoracic area. Radiological changes in lung parenchyma are observed in over 40% of SBRT patients ([Kimura 2006](#), [Timmerman 2018](#)).

Approximately a 25% of patients experience declines in DLCO, reported after a 5-fraction regimen SBRT ([Stone 2015](#)). Slow decline in lung function and radiological changes are described after SABR/SBRT leaving a small portion of patients (mean 10%) with persistent significant decline at one year, which can be difficult to distinguish from recurrence ([Huang 2012](#)). Both lung function testing and radiographical changes are directly related clinical scoring at 3 months ([Tadasuke 2020](#)), explaining a gradual change from radiological to functional and finally clinical symptomatic SBRT complication related to dose and volume treated.

Both radiological and clinical data are needed to create future guidelines around lung SBRT ([Mohamad 2018](#), [Tadasuke 2020](#), [Palma 2013](#)). Complementary drugs such as GC4711 may add important value by increasing efficacy and reducing pneumonitis risk.

